**Volume of Blood to Be Drawn From Each Subject**

Assessment	Sample volume (mL)	No. of samples	Total volume (mL)
Immune Studies	20	7	140
Additional Research Samples (with patient's consent per ICF)	20	7	140
Total: 280 ml			

Three additional samples of blood (120 ml) will be collected for each additional quad-shot treatment ( blood collection before starting radiotherapy and before each cycle of pembrolizumab administered before and after the quad-shot treatment)

**Withdrawal of informed consent for donated biological samples**

If a subject withdraws consent to the use of donated samples, the samples will be disposed of/destroyed, and the action documented.

**The Principal Investigator:**

- Ensures that biological samples from that subject, if stored at the study site, are immediately identified, disposed of /destroyed, and the action documented.
- Ensures the laboratory(ies) holding the samples is/are informed about the withdrawn consent immediately and that samples are disposed/destroyed.
- Ensures that the subject is informed about the sample disposal.

## **10.0 Pharmaceutical Information**

A list of the adverse events and potential risks associated with the investigational or commercial agents administered in this study can be found in Section 10.1.3.

### **Pharmaceutical Accountability**

Drug accountability logs will be maintained for all [investigative (if appropriate)] agents used under this protocol. These logs shall record quantities of study drug received and quantities dispensed to patients, including lot number, date dispensed, patient identifier number, patient initials, protocol number, dose, quantity returned, balance remaining, and the initials of the person dispensing the medication.

## 11.0 Statistical Considerations

### 11.1 Analysis of Primary Objective

11.1.1 For this pilot study, the primary analytic objective is to measure the overall response rate measured according to RECIST criteria and determine the percent of patients with either a partial or complete response (PR or CR) and the corresponding 95% Clopper Pearson exact confidence interval. This estimate will provide useful information concerning the potential efficacy of this treatment for planning future studies.

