### **5.0 Study Outcomes and Study Measures**

#### **5.1 Primary Outcome**

- 5.1.1 The overall response rate will be measured according to RECIST 1.1 (Section 7.1.3).

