### **6.6 Criteria for Removal from Study**

Patients will be removed from study when any of the following criteria apply:

Quad-Shot Radiotherapy in Combination with Immune Checkpoint Inhibition for Advanced/Recurrent Head and Neck Cancer  
Wake Forest Baptist Comprehensive Cancer Center  
WFBCCC60320

- Patient withdrawal of consent or loss to follow-up.
- Adverse event that, in the opinion of the investigator or the sponsor, contraindicates further dosing.
- Subject is determined to have met one or more of the exclusion criteria for study participation at study entry and continuing investigational therapy might constitute a safety risk.
- Pregnancy or intent to become pregnant
- Grade  $\geq 3$  infusion reaction.
- Subject noncompliance that, in the opinion of the investigator or sponsor, warrants withdrawal; eg, refusal to adhere to scheduled visits.
- Initiation of alternative anticancer therapy including another investigational agent.
- Confirmation of PD and investigator determination that the subject is no longer benefiting from protocol treatment.
- Death.

Subjects who are permanently discontinued from further receipt of investigational product, regardless of the reason (withdrawal of consent, due to an AE, other), will be identified as having permanently discontinued treatment.

Subjects who are removed from study prior to completing at least 2 cycles of ICI followed by at least 1 cycle of quad-shot radiotherapy followed by at least 2 cycles of ICI will be discontinued from the study and replaced.

Subjects who are permanently discontinued from receiving investigational product will be followed for safety until follow-up criteria are met in Section 6.4. Subjects who decline to return to the site for evaluations will be offered follow-up by phone for at least 60 days as an alternative.

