### 7.1.3 Response Criteria

- **Definition of complete response (CR)** for target and non-target lesions, as appropriate
  - Target Lesions:
    - Disappearance (or decrease to the point at which measurement is not possible) of all target lesions. **Any pathological lymph nodes (whether target or non-target) must have reduction in short axis to <10 mm** (the sum may not be “0” if there are target nodes)
  - Non-target lesions:
    - Disappearance (or decrease to the point at which measurement is not possible) of all non-target lesions. **All lymph nodes must be non-pathological in size (< 10 mm short axis)**
- **Definition of partial response (PR)** for target and non-target lesions, as appropriate
  - Target lesions:
    - At least a 30% decrease in the sum of diameters of target lesions, taking as reference the baseline sum of diameters
  - Non-target lesions
    - **Non-CR/Non-PD:** Persistence of 1 or more **non-target lesion(s)**.
- **Definition of progressive disease (PD)** for target and non-target lesions, as appropriate
  - Target Lesions:
    - > 20% increase in the sum of the longest diameters (SLD) taking as reference the smallest SLD recorded since the treatment started (nadir) **and minimum 5 mm increase over the nadir**
    - When sum becomes very small, increases within measurement error (2-3 mm) can lead to 20% increase
    - (Note: the appearance of one or more new lesions is also considered progressions)
  - Non-target lesions:
    - *Unequivocal progression* of existing non-target lesions. The appearance of one or more new lesions.
    - *Unequivocal progression* should not normally trump target lesion status. It must be representative of overall disease status change, not a single lesion increase
    - Although a clear progression of “non-target” lesions only is exceptional, the opinion of the treating physician should prevail in such circumstances, and the progression status should be confirmed at a later time by the review panel (or Principal Investigator).

- **Definition of stable disease (SD)** for target and non-target lesions, as appropriate
  - Target lesions:
    - Neither sufficient shrinkage to qualify for PR nor sufficient increase to qualify for PD, taking as reference the smallest sum diameters while on study
- **Definition and evaluation of best overall response**, if applicable  
The best overall response is the best response recorded from the start of the treatment across all time points.

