#### 7.1.4 Duration of Response

Duration of overall response: The duration of overall response is measured from the time measurement criteria are met for CR or PR (whichever is first recorded) until the first date that recurrent or progressive disease is objectively documented by clinical, radiographic, or pathologic findings (taking as reference for progressive disease the smallest measurements recorded since the treatment started).

The duration of overall CR is measured from the time measurement criteria are first met for CR until the first date that progressive disease is objectively documented.

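### The primary response rate counts a patient as a responder on one unconfirmed, investigator-read scan, and partial response has no millimetre floor against the stated measurement error

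*Combined protocol and SAP*

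**What the plan says.** Section 5.1 makes overall response rate (ORR) the primary outcome and refers to RECIST 1.1 as set out in Section 7.1.3. Section 11.1 will "determine the percent of patients with either a partial or complete response (PR or CR) and the corresponding 95% Clopper Pearson exact confidence interval".

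Section 7.1.3 states: "The best overall response is the best response recorded from the start of the treatment across all time points". Partial response (PR) is "At least a 30% decrease in the sum of diameters of target lesions, taking as reference the baseline sum of diameters". Neither that section nor its best-response table asks for a second scan or a minimum interval. Section 7.1.4 starts response duration when the criteria are first met.

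Progression (PD) is handled differently. The same section warns that "increases within measurement error (2-3 mm) can lead to 20% increase" and, besides the 20% rise, requires a "minimum 5 mm increase over the nadir".

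The principal investigator reads response, and independent review afterwards is optional (Section 7.1.6). Section 7.1 places response evaluation after 5 cycles and, for patients still on immunotherapy, after 10. Section 11.3 will weigh the result against earlier rates of 13-36%.

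**The concern.** A patient who meets PR or CR on one scan and not on the next remains a responder. Two things can produce such a read: real shrinkage that does not last, at any lesion size, and measurement error in small lesions. The plan recognises the second risk for progression and guards against it, but leaves PR open to it. At most two lesions enter the target sum (Section 7.1.1), so averaging helps little.

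The study has one arm, so no concurrent control shares the upward shift. The ORR is meant to inform future studies and to show whether they are warranted. A reader of the final report could not tell how many of the responses rest on a single read.

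**Working it through.** **1. The plan's own figure.** The Clopper-Pearson 95% interval for 7/15 is 0.213 to 0.734, a width of 0.5215. This reproduces the 0.52 in Section 11.3.

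**2. Weight of one response.** 1/15 = 6.7 points. For example, 4/15 = 26.7% (95% CI 7.8-55.1%) against 3/15 = 20.0% (4.3-48.1%). Against the 36% upper benchmark, 5/15 = 33.3% lies below it and 6/15 = 40.0% above it.

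**3. Threshold against stated error.** PR needs a fall of 0.30 × baseline sum:
- 10 mm (the CT measurability limit in Section 7.1.1): 3 mm, within the stated 2-3 mm
- 20 mm: 6 mm, outside it
- 40 mm: 12 mm, outside it

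Nodes must be at least 15 mm in short axis to be measurable, so a single nodal target needs a fall of at least 4.5 mm.

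**4. Noise alone.** Take one lesion whose true size T does not change, with independent normal error of SD s on the baseline and on each later scan. A false PR occurs when follow-up ≤ 0.7 × baseline, so the chance per scan is Φ(−0.3T / (s√(1 + 0.7²))). For T = 10 and s = 1.5 this is Φ(−3/1.831) = Φ(−1.64) = 5.1%. For two scans that share one baseline, the chance of at least one false PR is found by integrating over the baseline error. The documents give no SD, so s is an assumption, shown over a range:

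| True size | s = 1.0 mm | s = 1.5 mm | s = 2.0 mm |
|---|---|---|---|
| 10 mm | 1.4% | 9.3% | 19.3% |
| 12 mm | 0.3% | 4.7% | 12.7% |
| 15 mm | <0.1% | 1.4% | 6.1% |
| 20 mm | <0.1% | 0.1% | 1.4% |

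With s = 1.5 mm and both scans required to agree, the 10 mm and 12 mm figures fall to 0.8% and 0.3%. If immunotherapy continues and a third scan is read, the single-read figures at 10, 12 and 15 mm become 13.0%, 6.7% and 2.0%.

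**5. Effect on the ORR.** Suppose the true rate is 17% (pembrolizumab alone in one Table 1 study), every non-responder has one stable lesion of the given size, and s = 1.5 mm:
- 10 mm: 17 + 0.83 × 9.3 = 24.7%
- 12 mm: 17 + 0.83 × 4.7 = 20.9%
- 15 mm: 17 + 0.83 × 1.4 = 18.2%

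For a given s, the 10 mm line is an upper bound. The documents give no distribution of target sizes, and most patients may have larger lesions.

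**6. Timing.** Five cycles × 3 weeks = 15 weeks to the first scan (12-18 with the ±1 cycle window in Section 6.1), and 30 weeks to the second. Section 11.5 allows about 3 months (13 weeks) of response follow-up after accrual. For the last patients this is shorter than one nominal scan interval and leaves no room for a confirming scan.

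**The case against.** The best case for the plan is that this is a pilot with no hypothesis test and an interval up to 0.52 wide, so one misclassified patient is small beside sampling error. Target-lesion response duration is a secondary outcome and would expose short-lived target responses. Tumor measurements have their own form (Section 13.2), so a confirmed rate could be derived later. A genuine PR that ends is still a response. Table 1 does not say whether its rates are confirmed, so bias against the benchmark is not shown. Much of this stands: it limits the severity and argues against replacing the planned endpoint. It does not tell the reader how many responses rest on one read, and a confirmation rule chosen after the data are seen is weaker than one fixed beforehand.

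The citation of RECIST 1.1 might be taken to bring in a confirmation rule. Section 5.1 points to the criteria in Section 7.1.3, which contain none, and the documents cannot settle the question further.

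Three stronger readings are tempting but unsupported:
- *Progression must be confirmed and response need not be.* Section 6.6 does list "Confirmation of PD and investigator determination that the subject is no longer benefiting from protocol treatment", but as a reason for removal from study. The best-response table, the PFS definition, and the treatment-end rules in Sections 4.2 and 6.4 require no confirmation. In Section 7.1.3 only progression confined to non-target lesions is to be confirmed later. Any mismatch between Section 6.6 and Sections 4.2 and 6.4 is a separate matter to reconcile.
- *This is the trial's only efficacy figure.* Section 11.2 also lists target and non-target response, duration of response, PFS and OS.
- *About a third of responses would fail confirmation.* The background section's 5.7-month median control in responders, with exponential decay over 15 weeks (3.45 months), gives exp(−ln 2 × 3.45/5.7) = 0.66 retained. That figure comes from radiotherapy alone at the primary site, the curve is assumed, and it describes real responses ending rather than false ones.

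**Conclusion.** The point holds in limited form. As written, one investigator-read scan suffices for the primary ORR, and PR lacks the protection against measurement error that progression has. Any resulting bias in the estimate is upward, at 6.7 points per patient. With an assumed SD of 1.5 mm and two scans, noise produces a false PR in about 5-9% of stable 10-12 mm lesions and 1.4% at 15 mm. At SD 1.0 mm it is 1.4% or less throughout, and at SD 2.0 mm it reaches 6.1% at 15 mm. Transient shrinkage can occur at any size, but the documents give no rate for it, so neither the total bias nor a confirmed ORR can be predicted. With no formal test, the consequence is an optimistic estimate rather than type I error inflation. The change is worth making because it is cheap and shows how far the result depends on single reads.

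**What to change.** In Sections 7.1.3 and 11.1:
- Keep the best-response ORR as planned and state that it is unconfirmed.
- Add a confirmed ORR with its Clopper-Pearson interval: PR or CR criteria are still met at the next available scan at least 4 weeks later.
- Report separately the number of responders with no later scan, and count them as unconfirmed in the confirmed ORR. A rule is needed because the 10-cycle evaluation happens only if immunotherapy continues, and later imaging is discretionary (Sections 7.1 and 6.5).
- Show both rates wherever the result is compared with 13-36% or used for planning.

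In Section 11.5, align the 3 months of response follow-up with the 5-cycle scan interval.

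The cost is a few sentences, one derived variable and probably a longer stated study length. No scan beyond those already obtained is required, and n = 15 and the 0.52 width do not change. The downside is that the confirmed figure will be conservative: scans are about 15 weeks apart, so some genuine responses will have ended or will lack a later scan. It should therefore stand beside the planned ORR, not replace it.

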### 11.2 Analysis of Secondary Objective

There are 6 secondary outcomes of interest for this pilot study. These are 1) response rate for the target lesion; 2) response rate for non-target lesions 3) duration of response for the target lesion 4) progression free survival (PFS) 5) overall survival (OS) and tolerability assessed using PRO-CTCAE. We now describe our analytic approach for each measure.

For the response rate measures we will estimate the percent of responders (PR or CR) and the corresponding 95% Clopper Pearson exact confidence intervals. For the duration of response, among responders we will estimate both the mean and median duration and the corresponding 95% confidence intervals for the mean and inter-quartile range for the median. For time to event measures (PFS and OS) we will estimate Kaplan Meier survival curves and estimate the median time to event times as well as the percent PFS and OS at 6 months and 1 year post treatment. For tolerability, we will estimate the percent of patients with different AEs assessed using the PRO-CTCAE and corresponding 95% Clopper Pearson exact confidence intervals.

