### 2.1 Primary Objective(s)

2.1.1 Measure the overall response rate for immunotherapy given with quad-shot radiotherapy

### 2.2 Secondary Objective(s)

2.2.1 Measure the response rate at the target lesion.

Quad-Shot Radiotherapy in Combination with Immune Checkpoint Inhibition for  
Advanced/Recurrent Head and Neck Cancer  
Wake Forest Baptist Comprehensive Cancer Center  
WFBCCC60320

- 2.2.2 Measure the response rate at non-target sites *in patients with non-target sites.*
- 2.2.3 Evaluate the durability of response at the target lesion.
- 2.2.4 Evaluate progression-free survival.
- 2.2.5 Evaluate overall survival.
- 2.2.6 Assess the tolerability of the combination of quad-shot radiotherapy with immunotherapy in order to assess the feasibility of this treatment regimen.

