### 4.2 Study Design

This is a single-arm, non-randomized pilot study to evaluate the efficacy and tolerability of combination of **two standard of care interventions** (quad-shot palliative radiotherapy and pembrolizumab immunotherapy) for patients with advanced/recurrent/metastatic head and neck cancer.

Fifteen patients will be enrolled who have no curative localized treatment options, are eligible for palliative immunotherapy (pembrolizumab), have a lesion that can be targeted by radiotherapy, and are eligible for palliative radiotherapy as recommended by their radiation oncologist.

Quad-Shot Radiotherapy in Combination with Immune Checkpoint Inhibition for  
Advanced/Recurrent Head and Neck Cancer  
Wake Forest Baptist Comprehensive Cancer Center  
WFBCCC60320

Patients eligible for this study will be those scheduled to receive palliative immunotherapy with the immune checkpoint inhibitor pembrolizumab (which is standard of care) for advanced, R/M head and neck SCC according to standard of care practice. They will also be eligible for palliative quad-shot radiotherapy according to the standard of care for advanced/recurrent/metastatic HSNCC. Quad-shot radiotherapy will be applied between immunotherapy cycle 2-3 or between immunotherapy cycle 3-4, within the last week of the cycle, and not to be delivered on the same day as ICI administration. Up to two additional quad-shot cycles will be delivered between cycles 6-7 or 7-8 (prior to cycle 8) and 11-12 or 12-13 (prior to cycle 13) of immunotherapy. The additional quad-shot treatments will be delivered in a similar fashion, in the last week of the ICI cycle.

Restaging imaging with CT, MRI or PET/CT will be obtained every 5-6 immunotherapy treatments. For the purposes of lesion measurements, follow-up imaging must be performed using the same modality (CT or MRI) as was used for initial baseline imaging. PET/CT may be utilized for follow-up imaging at the clinician's discretion. The maximum response in the targeted lesion and in the non-targeted lesions will be assessed. Subsequent immunotherapy cycles will be delivered after quad-shot radiotherapy until tumor progression or treatment intolerance.

Palliative local (non-systemic) interventions to other sites that are not quad-shot radiotherapy target sites is allowable while on study protocol treatment for the management of cancer symptoms. This should not be utilized for progression of disease at that site.

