#### **5.2 Secondary Outcomes**

- 5.2.1 The response rate in the target lesion measured according to RECIST 1.1 (Section 7.1.3).
- 5.2.2 The response rate in the non-target lesions (if applicable) will be measured according to RECIST 1.1 (Section 7.1.3).
- 5.2.3 The duration of response at the target lesion will be defined as the duration from the time measurement criteria are met for CR or PR (whichever is first recorded) until the first date of recurrent or progressive disease as defined in Section 7.1.4.

Quad-Shot Radiotherapy in Combination with Immune Checkpoint Inhibition for  
Advanced/Recurrent Head and Neck Cancer  
Wake Forest Baptist Comprehensive Cancer Center  
WFBCCC60320

- 5.2.4 Progression-free survival (PFS) will be defined as in Section 7.1.5.
- 5.2.5 Overall survival (OS) will be defined as in Section 7.1.5.
- 5.2.6 Tolerability will be measured using the Patient-Reported Outcomes version of the Common Terminology Criteria for Adverse Events (PRO-CTCAE).

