#### 7.1.5 Survival Outcomes

Progression-Free Survival is defined as the duration of time from registration to the time of progression, death, or date of last contact; those lost to follow-up will be censored.

Overall Survival is defined as the duration of time from registration to date of death or date of last contact; those lost to follow-up will be censored.

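### Duration of response needs Kaplan-Meier estimation with a censoring rule, and 11.2 should time the PFS and OS percentages from registration

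*Combined protocol and SAP*

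**What the plan says.** Durability is a named secondary objective (2.2.3): "Evaluate the durability of response at the target lesion". Section 5.2.3 starts the clock at the first recorded CR or PR and runs it "until the first date of recurrent or progressive disease as defined in Section 7.1.4". Section 7.1.4, which defines the duration of overall response, runs it "until the first date that recurrent or progressive disease is objectively documented by clinical, radiographic, or pathologic findings".

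For the analysis, 11.2 states for patients who responded that "we will estimate both the mean and median duration and the corresponding 95% confidence intervals for the mean and inter-quartile range for the median". Its next sentence reads "For time to event measures (PFS and OS) we will estimate Kaplan Meier survival curves". It then adds medians "as well as the percent PFS and OS at 6 months and 1 year post treatment".

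The only censoring rule is in 7.1.5 and covers PFS and OS. That section also sets their origin: "Progression-Free Survival is defined as the duration of time from registration to the time of progression, death, or date of last contact". OS likewise starts at registration.

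**The concern.** A duration that ends only at recurrence or progression is a time-to-event measure. A responder still in response at the analysis has no end date. Neither 5.2.3, 7.1.4 nor 11.2 says what to do with that patient, with one lost to follow-up, or with one who dies without progression. Because 11.2 reserves Kaplan-Meier for PFS and OS, the natural reading is that duration gets an ordinary mean and median. Ongoing responses must then be either counted as ended at the cut or left out. Both pull the mean down, and the shortfall grows as responses lengthen. Two analysts could also report different values from the same data.

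The objective matters to the trial's argument. The background section gives short control at the treated site after quad-shot alone as part of the rationale for the combination.

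There is also a smaller mismatch: 7.1.5 starts PFS and OS at registration, but 11.2 times their percentages by reference to treatment.

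**Working it through.** The plan gives no figure for duration to reproduce. Its only precision figure, a maximum confidence-interval width of 0.52 for 15 patients (11.3), does reproduce: the exact interval at 7/15 is 0.2127 to 0.7341, width 0.5215. It concerns response rates and is untouched by this point.

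**Inputs from the documents**
- Accrual of 21 months, with the study called complete at about 24 months (11.5).
- First response scan after 5 three-week cycles (7.1, Schema): 15 weeks = 3.45 months.
- Median duration of control of 5.7 months at the primary for CR/PR in an earlier quad-shot study (background section).

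**Assumptions**
- Uniform accrual, response dated at 15 weeks, exponential durations, no deaths.
- Two possible cuts, since none is stated: month 24 (from 11.5), and month 33 (21 + 12), the earliest at which the last patient could have one year of follow-up for the 1-year percentages in 11.2.

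**Formulas.** Let λ = ln 2 / 5.7 = 0.1216 per month, so the true mean is 1/λ = 8.2 months. Follow-up after response, F, is uniform between a and b.
- Share ongoing = (e^(−λa) − e^(−λb)) / (λ(b − a)).
- Simple mean with ongoing responses counted as ended = (1 − share ongoing) / λ.
- The simple median solves e^(−λt) × P(F > t) = 0.5.

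**Month 24.** Here b = 24 − 3.45 = 20.55 and a = 0 (the few patients not yet scanned drop out).
- Share ongoing: (1 − 0.082) / 2.499 = 0.367.
- Mean: 0.633 × 8.22 = 5.2.
- Median: 3.95, since e^(−0.480) × (1 − 3.95/20.55) = 0.619 × 0.808 = 0.50.

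**Month 33.** Here a = 33 − 21 − 3.45 = 8.55 and b = 29.55.
- Share ongoing: (0.354 − 0.027) / 2.554 = 0.128.
- Mean: 0.872 × 8.22 = 7.2.
- Median: 5.7, unbiased, because every responder has at least 8.55 months of follow-up.

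| True median | Cut | Ongoing | Mean / median, counted as ended | Mean / median, dropped | True mean |
|---|---|---|---|---|---|
| 5.7 | 24 | 37% | 5.2 / 3.9–4.0 | 4.5 / 3.5 | 8.2 |
| 5.7 | 33 | 13% | 7.2 / 5.7 | 6.0 / 4.7 | 8.2 |
| 12 (assumed) | 24 | 59% | 7.2 / 6.0 | 5.6 / 4.6 | 17.3 |
| 12 (assumed) | 33 | 35% | 11.2 / 10.4 | 8.0 / 6.8 | 17.3 |

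**How many patients.** In Table 2, CR plus PR runs from 6 + 47 = 53% to 24 + 62 = 86%, or about 8 to 13 responders of 15. At a 5.7-month median, month 24 would leave 2.9 to 4.8 of them ongoing on average, and month 33 would leave 1.0 to 1.7.

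**Death without progression.** Suppose it has a 12-month median (assumed, and probably high, because it uses all deaths).
- Counted as an event, the median becomes 1/(1/5.7 + 1/12) = 3.9 months.
- Censored, it stays at 5.7.
- As a competing risk, cumulative progression reaches 50% at 7.5 months.
- With an assumed 24-month median the three values are 4.6, 5.7 and 6.4.

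**Which progression.** Section 5.2.3 concerns the target lesion but borrows its end date from 7.1.4, which concerns overall response, and 7.1.3 counts new lesions as progression. The text does not settle whether a new lesion elsewhere ends target-lesion duration.

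**Origin of the percentages.** Baseline scans precede registration (7.1) and fall at most 14 + 5 days before first treatment (6.1, note f). Registration and first treatment therefore differ by at most 19 days, or 0.62 months. Reading the registration curve that much later, with a 12-month median OS, gives 2^(−6.62/12) = 68.2% against 70.7% at 6 months, and 48.2% against 50.0% at 1 year. If the origin itself moves to first dose, the same exponential model gives no change.

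**The case against.** The strongest reply is that 11.2 is silent, not wrong. A median with quartiles can be read off a Kaplan-Meier curve, and nothing forbids that for duration. This stands in part: simple summaries are inferred from the contrast with PFS and OS. But a mean with a confidence interval cannot be computed for ongoing responses without a rule that the plan lacks.

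Second, month 24 is the least favourable case. The 1-year percentages and the follow-up until death in 6.5 point to a later cut. This stands. By month 33 the median is unbiased if ongoing responses are counted as ended, and the mean falls short by about one month.

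Third, sampling error is larger than the bias. At month 24 with 13 responders, correctly censored Kaplan-Meier medians spread from about 2.3 to about 15 or 16 months (central 95% of simulated trials). The disputed shift in the median is 5.7 − 3.95, about 1.8 months. This also stands, and is a reason to report individual durations. It does not justify adding an avoidable bias in a known direction.

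Fourth, the plan makes no formal comparison with earlier quad-shot data, and the documents do not say how the 5.7 months was calculated. A claim that a real gain would be hidden from readers is therefore conjecture.

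On the percentages, a reader might infer that survival will be counted from the last dose and so be badly distorted. The documents do not support that as the intent. Section 4.2 says "Subsequent immunotherapy cycles will be delivered after quad-shot radiotherapy until tumor progression or treatment intolerance", so for many patients the clock would start at the PFS event itself. Loose wording for time after treatment starts is likelier.

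**Conclusion.** The concern holds as a choice of method that should be corrected. Duration of response is a time-to-event measure for which 11.2 gives simple-looking summaries and no censoring rule. If they are computed as simple summaries, the mean is biased low whenever responses are ongoing. The median is biased low only if ongoing responders are dropped or the cut is early.

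A reader might infer that the plan commits to a biased estimator, or that durability will be understated by three months. The documents support neither: the handling is unstated, the cut is unstated, and the three-month shortfall in the mean (8.2 − 5.2) belongs to one illustrative scenario resting on exponential durations, uniform accrual and no deaths.

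The mismatch over the origin of the PFS and OS percentages is a wording error with a small or nil numerical effect. These endpoints are secondary and descriptive in a pilot without hypothesis tests. The primary response-rate analysis and the sample size are unaffected.

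**What to change.** In 11.2:
- Estimate duration of response by Kaplan-Meier, giving the median with a 95% confidence interval, and drop the simple mean.
- Censor responders without the event at their last tumour assessment.
- Report the number of ongoing responses and list the individual durations.
- Choose one primary handling of death without progression (event, censored or competing risk) and show an alternative as a sensitivity analysis. Note that counting death as an event makes local durability a composite.
- Time the PFS and OS percentages at 6 months and 1 year after registration.

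In 5.2.3, state whether the event is progression at the irradiated target lesion only, or any RECIST progression including new lesions. Without this, the censoring rule has no defined event.

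The cost is a few sentences and no new data. The drawback is imprecision: with few responders the Kaplan-Meier median may not be reached. Under the assumptions above, at a month-24 cut that happens in about 2 to 5% of simulated trials with 8 to 13 responders at a 5.7-month median, and in about 27 to 32% at an assumed 12-month median. The count of ongoing responses and the individual durations then carry the information.
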